Blinding: In light of the time-sensitive, point-of-care nature of the intervention being proposed, the patient, clinical team, and members of the study team involved in the RBC washing procedure will not be blinded to the patient’s treatment allocation status. Blinding will be ensured for Drs. [name] and [name] who will be running the proposed biomarker analyses.

Other aspects of care: ARDSnet trials have demonstrated the benefit of standardizing clinical processes in ICU trials.^{75,76} In this study, clinical care that may affect development of respiratory dysfunction and associated outcomes will be standardized to the extent possible. To this end, our protocol will specify optimal ventilator strategies for both the OR and ICU environments (tidal volume \leq 8 mL/kg predicted body weight; peak inspiratory pressures $<$ 35 cm H₂O, PEEP \geq 5 cm while ventilated in the ICU). Similarly, although we will not pre-specify RBC transfusion thresholds in this protocol, we will advise restrictive transfusion practices in the postoperative period (hemoglobin target $>$ 8 g/dL in the absence of acute bleeding and/or ischemia). This transfusion threshold was chosen as it is the current standard of care at the two participating institutions. Standardization of best practices in at-risk patients will decrease the heterogeneity of the risk modifiers that may otherwise confound our associations of interest (RBC washing and intermediate markers of respiratory outcomes). Additionally, each center has adopted protocols on daily spontaneous awakening and spontaneous breathing trials to facilitate standardized weaning from ventilators (see attached appendix for specific protocols). Non-intubated patients will undergo standard titration of oxygen twice daily (at 0700 and 1900, +/- 2 hours). Patients saturating 92% or greater on room air will not receive supplemental oxygen, unless specifically requested by the primary service. If the primary care service requests oxygen supplementation for a patient saturating greater than or equal to 92% on room air, the reason for the deviation from oxygen weaning will be documented. Patients will continue to undergo evaluation for oxygen titration until liberation from oxygen therapy for 24 hours, hospital day 28, or hospital discharge, whichever comes first.

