Specific Aim 3: To facilitate the design and conduct of future clinical trials, we will also pursue a number of exploratory clinical outcomes. **The clinical outcome measure of interest for aim 3** is the duration of postoperative mechanical ventilation. Study coordinators will collect data daily until endotracheal extubation, death or hospital discharge regarding the need for mechanical ventilation. The primary clinical outcome will then be determined by calculating the duration of mechanical ventilation in hours for each study participant, determined by subtracting the time of ICU admission from the time of endotracheal extubation. If the study participant is extubated prior to ICU admission, the duration of mechanical ventilation will be assigned as 0 hours. Recognizing the potential for early death (intraoperative or early postoperative) biasing our primary clinical outcome, the number of ventilator free days (VFD) at postoperative day 28 will also be determined. Those who die prior to day 28 will be determined to have had 0 VFD. Those who are discharged from the hospital alive prior to day 28 will be assumed to have had no additional days of mechanical ventilation following hospital discharge. Additional secondary outcomes for Aim 3 will include evaluations of hypoxemia (SpO_2 , PaO_2/FiO_2), duration of oxygen supplementation, sequential organ failure assessment scores, and durations of ICU and hospital stay. The clinical diagnoses of TRALI, possible TRALI, and/or TACO will be measured through study day 5, or hospital discharge, whichever comes first.

Specimen Handling and Laboratory Assays: Aim 1b: 5 ml of blood will be drawn from each study participant at baseline, following the first RBC unit administered, 6 hours after the end of the first RBC transfusion, 18 hours after the end of first RBC transfusion, and on hospital day 5 if the patient remains hospitalized (see **Specific Aim 1** and **Specific Aim 2** for more details on the timing of blood draws). These safety laboratory

Table 6. Physiologic parameters to be measured during the study intervention period.	
Respiratory Variables	Hemodynamic Variables
PaO_2 , SpO_2 , FiO_2	Mean arterial pressure
Tidal Volume	Heart Rate
Peak inspiratory pressure	Cardiac output
Plateau airway pressure	Central venous/right atrial pressure
Positive end-expiratory pressure	Pulmonary artery wedge pressure

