Aim 3 will utilize standard analytical measures for comparing randomized treatment groups with ITT. For data that may be skewed (e.g., length of ventilation, ICU stay), Wilcoxon rank sum tests will be used to compare groups. Serial measurements (oxygen saturation) will be analyzed using longitudinal summary statistics (e.g., AUC, mean value). It should be noted that the intermediate clinical outcomes are not being powered for in this study. Estimates of precision (confidence intervals) along with range of responses will be used to guide subsequent trial designs (e.g. a larger phase II/III trial with clinical outcomes as the primary outcome of interest).

Additional statistical considerations: Consistent with early phase clinical trials, we have selected a level of significance higher than the traditional 0.05. This will facilitate advancement of the technique should it prove feasible and demonstrates potential efficacy. It is noted that multiple testing may increase the overall family wise error rate, so further research, particularly with clinical events, will be needed to quantify clinical efficacy of the approach. Missing data is expected to be minimal during the course of the study given the close surveillance the surgical and ICU environment provides. Missing specimens may occur in the event of patient discharge, death or administrative issues. Initial analyses will be conducted under the assumption of MCAR/MAR (ignorable missing). Sensitivity analyses using multiple imputation and pattern mixture models will be used to assess the robustness of the model assumptions. The analysis of specific aim 2 proposes to use a modification of the ITT principle. Justification for this is that it is a mechanistic aim with blinded examiners. We are interested in quantifying the effects of washing as clearly (and perhaps ideally) this is an early phase trial. In Aim 3, the clinical outcomes will be assessed using the traditional ITT definition to provide a more realistic measure of the effect size for planning subsequent studies.

Protocol Addendum:

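### The ventilator-free-day rule credits every remaining day to any patient discharged alive, even one still ventilated, and ventilation duration has no value for that patient

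*Combined protocol and SAP*

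**What the plan says.** All references are to the combined protocol and SAP.

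- **Ventilation duration.** Outcome Measures, Specific Aim 3, makes this the primary clinical outcome of the aim. It is calculated by "subtracting the time of ICU admission from the time of endotracheal extubation".
- **End of collection.** In the same paragraph: "Study coordinators will collect data daily until endotracheal extubation, death or hospital discharge regarding the need for mechanical ventilation".
- **Ventilator-free days.** Because early death could bias ventilation duration, "the number of ventilator free days (VFD) at postoperative day 28 will also be determined". Two scoring rules follow. For deaths: "Those who die prior to day 28 will be determined to have had 0 VFD". For live discharges, without exception: "Those who are discharged from the hospital alive prior to day 28 will be assumed to have had no additional days of mechanical ventilation".
- **Oxygen.** Duration of oxygen supplementation is named as a secondary Aim 3 outcome, with no formula. Other aspects of care says that evaluation for oxygen titration continues "until liberation from oxygen therapy for 24 hours, hospital day 28, or hospital discharge, whichever comes first".
- **Analysis.** The Aim 3 paragraph of the statistical section specifies intention to treat. For skewed data, with length of ventilation and ICU stay as the examples, "Wilcoxon rank sum tests will be used to compare groups". It says that these outcomes are not powered and that the estimates will guide later trial designs.

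**The concern.** The three events that end ventilation data collection are "until endotracheal extubation, death or hospital discharge". Listing discharge separately from extubation allows a patient to leave while still ventilated, for example by transfer to another facility. The live-discharge rule then treats the rest of the 28 days as free of ventilation, although nothing was observed to support that.

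The plan has already dealt with one poor outcome that cuts observation short: death before day 28 scores 0. Discharge on a ventilator also cuts observation short, but it is scored as if the patient had been extubated. VFD was added to cover a weakness in ventilation duration, yet for this patient the main outcome is undefined and its companion takes a favorable value.

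Aim 3 is meant to deliver estimates for planning the next trial, so a scoring error goes straight into what it produces. The clinical team is not blinded (Blinding), so discharge timing or support at discharge could differ by arm.

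**Working it through.** The documents give no figure that depends on this rule, so there is nothing to reproduce. The check applies the rule as written.

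**Inputs.** From Specific Aim 3: a 28-day horizon, no ventilation assumed after live discharge, and 0 VFD for death before day 28. From Study population: 154 transfused patients, or 77 per arm if split equally. Assumptions, because the documents are silent: a share p of 1–5% of an arm leaves ventilated (0.01 × 77 = 0.8 to 0.05 × 77 = 3.9 patients), on day d between 7 and 21, after continuous ventilation to that day.

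**Step 1: one patient.** Scored VFD = 28 − d. If ventilation continues to day 28, true VFD = 0.

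| Discharged ventilated on day | VFD as scored | VFD if ventilated to day 28 |
|---|---|---|
| 7 | 21 | 0 |
| 10 | 18 | 0 |
| 14 | 14 | 0 |
| 21 | 7 | 0 |

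A patient extubated on day d who stays off the ventilator receives the same 28 − d, so the score cannot tell the two apart.

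**Step 2: one arm's mean.** If all such patients stay ventilated to day 28, the overstatement is p × (28 − d).

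| p | d = 7 | d = 14 | d = 21 |
|---|---|---|---|
| 1% | 0.21 | 0.14 | 0.07 |
| 2% | 0.42 | 0.28 | 0.14 |
| 5% | 1.05 | 0.70 | 0.35 |

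These are upper values for each p and d. A patient weaned on day w after transfer has true VFD of 28 − w, so the overstatement is only w − d.

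**Step 3: the arm comparison.** The bias in the difference is the difference between the two arms' overstatements. With equal p and d it is zero. With 5% in one arm and 1% in the other, both at d = 14, it is 0.70 − 0.14 = 0.56 days in favor of the arm with more ventilated discharges.

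**Step 4: ventilation duration.** The formula needs an extubation time, and collection has stopped without one. Additional statistical considerations discusses missing data in general and names missing specimens; it gives no rule for a duration cut off by discharge.

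**Step 5: oxygen.** Liberation and discharge are listed as separate reasons to stop titration checks, and the outcome has no formula. No scored value can be computed for a patient who leaves on oxygen, because no scoring rule exists.

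**The case against.** **The consequence is small.** Aim 3 is exploratory and unpowered, and VFD supplements another outcome. Table 4 excludes emergency surgery, prevalent lung injury, hydrostatic edema and planned assist devices, so ventilated discharge may be rare. Nothing shows that it would differ by arm. All of this stands and limits the size of the point. It does not make the score correct.

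**Zero is not always the true value.** This also stands. A patient transferred on day 14 and extubated on day 18 has 28 − 18 = 10 VFD. The current rule gives 14 (4 too many) and a score of 0 gives 10 too few. Zero is exact only if ventilation, or death, runs through the window.

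**Stronger readings that the documents do not support:**

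- *These patients rank among the better ones.* A reader might infer this, but no VFD distribution is given. The Problem statement puts ventilator support in TRALI at typically 3 to 10 days. A survivor ventilated for 10 days scores 18 and still ranks above the transferred patient's 14. In a rank test, moving 14 to 0 changes that patient's order only relative to deaths and to survivors with 14 or fewer VFD.
- *The plan scores discharge on oxygen as a completed wean.* The text says when titration checks stop and never equates discharge with liberation. A duration cut at discharge is a likely default, but it is an inference. The exclusion of home-oxygen users concerns baseline use only.
- *Some 10 to 19 patients are misplaced on oxygen duration.* That would need an assumed 5–10% of 190 discharged on oxygen. The rate has no source in the documents, 190 is the upper limit for randomization, and the count presumes the unwritten scoring rule.

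**Conclusion.** The point holds for ventilation. Followed as written, the live-discharge rule gives a patient who leaves ventilated the same VFD as one extubated that day, and the primary clinical outcome of Aim 3 has no value for that patient. The VFD error is up to 28 − d days for the patient and up to 0.07–1.05 days in an arm's mean. The range for the mean rests on the assumed 1–5% frequency, discharge on days 7–21 and ventilation through day 28. Bias between arms needs a difference in the frequency or timing of ventilated discharge, for which the documents offer no evidence either way.

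For oxygen the finding is narrower: a rule is missing, and no wrong rule is stated. The correction is worth making because Aim 3 exists to supply estimates and the change is cheap, but it does not threaten the trial's main mechanistic aim.

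**What to change.** 1. **VFD.** Apply the no-additional-days assumption only to patients off the ventilator at discharge. Score those discharged or transferred while ventilated as ventilated through day 28 (0 VFD), and repeat the analysis under the current rule as a sensitivity analysis. For a patient continuously ventilated to discharge, the two scores bracket the true value, which lies between 0 and 28 − d.
2. **Ventilation duration.** State that it has not ended at discharge for these patients: either censor it there or, for the rank test, place them longest among survivors.
3. **Oxygen.** Record oxygen status at discharge and do not analyze patients who leave on oxygen as weaned that day. One option is time to liberation, with these patients counted as not liberated.

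The cost is a few sentences and a form item for oxygen status at discharge. Ventilation need is already collected daily to extubation, death or discharge, so ventilated discharges can be identified without follow-up after discharge. The small downside is that 0 VFD is conservative for a patient weaned soon after transfer; the sensitivity analysis shows how much that matters.

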Figure 4. RBC microparticle counts before (left) and after (right) washing with the CATS.

[figure not shown]
[figure not shown]
[figure not shown]

Figure 4. Lung injury biomarkers in patients who do and do not develop ARDS.

PHASE I/II CLINICAL TRIAL EVALUATING POINT-OF-CARE RBC WASHING TO PREVENT RBC-ASSOCIATED RESPIRATORY COMPLICATIONS FOLLOWING CARDIAC SURGERY

Study population: Study procedures are summarized in Figure 5. We will enroll a total 154 patients receiving at least one RBC transfusion on the operative day. We anticipate this will require randomizing up to **190 patients** in this trial (95 per group). Adult patients (age ≥ 18) who are planned to undergo cardiac surgery at one of the two participating institutions and who have a predicted RBC transfusion requirement of ≥ 4 units will be screened for the exclusion criteria outlined in Table 4. Predicted RBC transfusion requirements will be determined utilizing a recently published large-volume blood transfusion (LVBT) prediction model (>4 units of RBC).⁷³ A cut off of 4 predicted units of RBC administration was chosen because: 1) this transfusion volume has been associated with increased risk of pulmonary complications following cardiac surgery⁵⁸; 2) we have previously identified this transfusion volume as a common “dose” in patients who experience TRALI and/or TACO^{28, 39,42}; and 3) this threshold would still identify a sizable cardiac surgery population, ensuring study feasibility.

Study procedures:

Screening: Study coordinators will screen all adult (age ≥ 18) patients who are scheduled to undergo coronary artery bypass graft surgery with or without valve repair/replacement, complex cardiac valve surgery, pericardial resection, and/or ascending aortic surgery in one of the two participating institutions. Eligible patients with a predicted transfusion requirement of 4 or more units will be approached before their elective surgical procedure by a study coordinator for consent. After confirming the patient's inclusion and exclusion criteria, the study coordinator at the respective institution will obtain informed consent and assign a study ID number to the study participant. Screening logs will be maintained at each site to allow generation of a CONSORT diagram.

Table 4. Exclusion criteria.

Exclusion Criteria	Justification
• Emergency surgery	Inability to randomize/perform study procedures
• IgA deficiency	Not ethical to randomize to standard issue RBCs

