Statistical Considerations (prepared in collaboration with our statistical: Aim 1 is centered on the clinical and technical feasibility of on-demand RBC washing (hypothesis 1a). Feasibility is defined as the administration of protocol RBCs instead of "off-protocol" standard-issue RBCs. Simon's two-stage design will be used to determine if the protocol needs to be modified to prepare RBCs prior to the surgical procedure. The null hypothesis rate for feasibility is $p \leq 0.75$ versus the alternative that $p \geq 0.90$, where p is the probability of successfully preparing and administering the intervention RBCs. Stage 1 of the design will examine the first 16 cases randomized to RBC washing. If 12 or fewer transfusions were deemed "feasible", the protocol will be modified to pre-wash RBCs (see limitations). If 13 or more are feasible, an additional 32 cases will be evaluated. Should 39 or fewer (of the 48 studied) not be feasible, the protocol will be modified to pre-wash. If 40 or more cases meet the feasibility definition, the remainder of the study will go as originally planned. (Sample size/ design calculations details: PASS 2008, alpha=0.10, beta=0.10, Optimal design). The safety endpoint for aim 1 is the change in hemoglobin level (hypothesis 1b). The change in hemoglobin after the first transfused unit will be used as the primary safety measure. Wilcoxon rank sum tests will be used to compare change in hemoglobin levels between randomized groups. The change in concentrations of soluble BRMs (e.g.

neutral lipids; hypothesis 1c) will be assessed using paired t-tests. There is > 80% power to detect a 0.4 SD difference pre- to post-washing with 78 washed RBC products. Should there be fewer (due to feasibility), power will decrease. However, the magnitude of differences observed in preliminary data (92% reduction, Figure 4) is many times larger than an effect size of 0.4. Therefore, power for this hypothesis should not be a concern.

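### The stage 2 feasibility rule is reversed by the word *not*: as written it is always met and contradicts the sentence after it

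*Combined protocol and SAP*

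**What the plan says.** Statistical Considerations (Aim 1, hypothesis 1a) sets a null feasibility rate of at most 0.75 against an alternative of at least 0.90, "where p is the probability of successfully preparing and administering the intervention RBCs". The design inputs are alpha 0.10, beta 0.10 and the Optimal criterion.

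The rule then runs in four steps:

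- Stage 1 size: "Stage 1 of the design will examine the first 16 cases randomized to RBC washing".
- Stage 1 boundary: the sentence opening "If 12 or fewer transfusions were deemed" sends a count of 12 or fewer feasible to pre-washing. Otherwise: "If 13 or more are feasible, an additional 32 cases will be evaluated".
- Stage 2, modify: "Should 39 or fewer (of the 48 studied) not be feasible, the protocol will be modified to pre-wash".
- Stage 2, continue: "If 40 or more cases meet the feasibility definition, the remainder of the study will go as originally planned".

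The outcome being counted is described in one sentence, which begins "Feasibility is defined as the administration of protocol RBCs instead of" and goes on to name off-protocol standard-issue units. The stage 1 boundary speaks of transfusions. The stage 1 size, the stage 2 size and the continue sentence all speak of cases.

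**The concern.** Three of the four boundary statements count successes: the two stage 1 branches and the stage 2 continue rule. The stage 2 modify rule alone counts failures, yet it keeps the number 39, which makes sense only as a count of successes. Taken at its word, it sends the trial to pre-washing whatever happens at stage 2. It also applies at the same time as the continue rule whenever 40 or more cases are feasible.

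This is the plan's operative rule for changing how the intervention is delivered, and Sample Size Considerations says that the final sample size may be adjusted on what the two-stage design finds. A decision threshold that points both ways should not stand in the plan, even when the intention can be worked out.

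A smaller point sits beside it. The change of noun from cases to transfusions leaves the counting unit less clear than it should be in patients chosen for a high expected number of units: "Eligible patients with a predicted transfusion requirement of 4 or more units will be approached before their elective surgical procedure".

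**Working it through.** **Inputs**, all from Statistical Considerations, Aim 1: p0 = 0.75, p1 = 0.90, alpha = 0.10, beta = 0.10, Optimal design; n1 = 16, r1 = 12 (go on at 13 or more feasible); 32 further cases, n = 48; final boundary r = 39 (continue at 40 or more feasible).

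**1. Reproduce the plan's design, counting feasible cases throughout.**

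P(continue | p) = sum over x = 13 to 16 of P(X1 = x) × P(X2 ≥ 40 − x), with X1 ~ Bin(16, p) and X2 ~ Bin(32, p).

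| x | X2 needed | P(X1 = x), p = 0.75 | P(X2 ≥ 40 − x) | product | P(X1 = x), p = 0.90 | P(X2 ≥ 40 − x) | product |
|---|---|---|---|---|---|---|---|
| 13 | 27 | 0.2079 | 0.1530 | 0.0318 | 0.1423 | 0.9056 | 0.1289 |
| 14 | 26 | 0.1336 | 0.2779 | 0.0371 | 0.2745 | 0.9642 | 0.2647 |
| 15 | 25 | 0.0535 | 0.4325 | 0.0231 | 0.3294 | 0.9883 | 0.3256 |
| 16 | 24 | 0.0100 | 0.5935 | 0.0060 | 0.1853 | 0.9967 | 0.1847 |
| Sum | | 0.4050 | | **0.0980** | 0.9316 | | **0.9039** |

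(Sums are of unrounded terms.) The exact type I error is 0.098, within 0.10. The power is 0.904, above 0.90.

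Expected size at p = 0.75: 16 + 32 × 0.4050 = 28.96.

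A search over total sizes 20 to 69, requiring type I error at most 0.10 and power at least 0.90, returns 12/16 then 39/48 as the design with the smallest expected size at p = 0.75. The runner-up is 13/17 then 42/52, at 29.36. So the stated boundaries are those of the Optimal design, and 39 is a count of feasible cases.

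**2. Apply the stage 2 modify sentence as written.**

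- Stage 2 requires at least 13 of 16 feasible, so at most 16 − 13 = 3 stage 1 cases are not feasible.
- If all 32 stage 2 cases also fail, the total not feasible is 3 + 32 = 35.
- 35 is below 39, so the condition of 39 or fewer not feasible holds for every possible stage 2 result.

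Followed literally, the sentence gives modification with probability 1 at any p. Stage 1 failures are modified by the stage 1 rule, and all others by this one.

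**3. Set it against the next sentence.**

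Take 40 feasible of 48, so 48 − 40 = 8 not feasible. Eight is 39 or fewer, so the modify rule applies. Forty is 40 or more, so the continue rule applies too. The two conflict in exactly the results that should lead to continuation: probability 0.904 at p = 0.90 and 0.098 at p = 0.75.

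**4. Delete *not*.**

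The modify rule becomes 39 or fewer feasible and the continue rule stays at 40 or more. The two are then complementary, and the operating characteristics are those of step 1.

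**The case against.** The strongest reply is that this is a slip which the text itself resolves. The rate p is defined as a probability of success, both stage 1 branches count successes, and the very next sentence gives the correct continue rule. Because the literal condition can never fail at stage 2, nobody could apply it as a real decision rule. The rule also tests neither efficacy nor whether the trial stops; it chooses between two ways of preparing the cells. All of this stands, and it is why the point is a wording correction. It does not remove the contradiction from the decision threshold.

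Two stronger readings are tempting, and the documents do not support them.

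- A reader might infer that the feasibility design has the wrong boundaries or error rates. It does not: the stated boundaries reproduce exactly from the stated inputs.
- A reader might infer that the mixture of transfusions and cases invalidates the design's alpha and power, so that the boundaries need deriving again. The text favours the patient as the unit: stage 1 takes cases as randomised, and randomisation is at consent. The per-transfusion off-protocol proportion in Outcome Measures can stand beside a patient-level rule. A patient may receive both washed and emergency off-protocol units, and the available text does not expressly say how that patient is scored. However, defining feasibility as protocol cells in place of off-protocol ones already leans against counting a patient as feasible because a single unit was washed. Any figure for the effect of scoring would need unit counts, per-unit rates and within-patient correlation, none of which the documents give. The stage 1 sentence also refers to a limitations discussion that is not in the text available for review.

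**Conclusion.** Wrong as written. The stage 2 modify sentence is met by every trial that reaches stage 2 (at most 35 of 48 can be not feasible, against a threshold of 39), and it contradicts the continue sentence whenever 40 or more are feasible. The error is one word. Once it is removed, the plan's own design stands in full: type I error 0.098, power 0.904, expected size 28.96 at p = 0.75.

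The reversal and the contradiction follow from the plan's integers alone and need no assumption. The operating characteristics rest on the usual one of independent cases with a common feasibility rate.

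The documents do not show that the reversed wording was ever applied, so nothing here implies that a decision in the trial was wrong. The counting unit is a matter of consistency and reporting. It is not a ground for redefining a case or changing the boundaries.

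**What to change.** 1. In the stage 2 modify sentence, delete *not*, so that 39 or fewer feasible of 48 leads to the modification and 40 or more leads to continuation as planned. Cost: one word. All boundaries and both stage sizes stay as they are.
2. In the stage 1 boundary sentence, replace the word transfusions with cases, to match the rest of the rule. Cost: one word.
3. When the feasibility result is reported, state how patients who received both washed and off-protocol units were scored. The Protocol Addendum shows that the first 75 washed units have been analysed. Since 75 / 16 = 4.69, those units came from at least 16 patients if the mean was 4.6 or fewer washed units per patient, so stage 1 may well be over. The request is therefore to report the scoring as it was applied. A scoring rule chosen now should be labelled post hoc. Cost: one sentence in the report.
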